This material is the property of the NYU Langone. Do not disclose or use except as authorized in writing by the study sponsor
Observational Study Template Version: 8 February 2019

QA	Quality Assurance
QC	Quality Control
RAVLT	Rey Auditory Verbal Learning Test
RIS	Radiologically isolated syndrome
RS-fMRI	Resting State-fMRI
RT	Reaction Time
SAE	Serious Adverse Event/Serious Adverse Experience
SDMT	Symbol Digit Modalities Test
SES	Socioeconomic Status
SOP	Standard Operating Procedure
tDCS	Transcranial Direct Current Stimulation
UAP	Unanticipated Problem
US	United States
ISD	Intraindividual Standardized Deviations

CONFIDENTIAL

This material is the property of the NYU Langone. Do not disclose or use except as authorized in writing by the study sponsor
Observational Study Template Version: 8 February 2019

Protocol Summary

[figure not shown]
Title	Intra-Individual Variability (IIV) in Cognitive Performance as a Marker of Prodromal Disability in MS
Short Title	IIV Cognitive biomarkers in early MS
Funding Sponsor	National Multiple Sclerosis Society (NMSS)
Brief Summary	
We recently received notice of award for the proposed study. The focus of this work is the evaluation of a measure of cognitive functioning- intra-individual variability (IIV) – derived from a computer-based continuous reaction time (RT) task (Cogstate) as an early marker of prodromal MS.
 
This study is a prospective observational clinical study, where we will recruit adults with early MS (n=60) to complete a cognitive assessment and an optional gait assessment using Runscribe and G-sensor. Thirty-five [35] participants will also have a single 60-minute investigational MRI combined with 20 minutes of simultaneous tDCS. The MRI will repeat the protocol from our current study (ClinicalTrials.gov Identifier: NCT03564496, IRB i18-00548) using simultaneous transcranial direct current stimulation (tDCS) during the imaging acquisition.

Objectives	To evaluate cognitive IIV as marker of prodromal MS
Methodology	Observational study
Endpoint	
- Primary outcomes: Cogstate Brief Battery (CBB) measures of reaction time/accuracy/IIV and Cerebral metabolic rate of oxygen (CMRO₂)- Secondary outcomes: Brief International Cognitive Assessment for MS (BICAMS) and IIV in gait measured with inertial wearable sensors (optional)
Study Duration	24 months
Participant Duration	Participation will include one visit that will last approximately 1.5-3.5 hours and will include a cognitive assessment, optional gait assessment. 35 participants will have a 60-minute MRI combined with simultaneous tDCS after the cognitive assessment. Participants may complete the MRI during a second visit.
Population	We will recruit 50 adults with early (prodromal) MS (e.g., clinically isolated syndrome (CIS), radiologically isolated syndrome (RIS), or subjects with a MS diagnosis of less than 5 years).
Study Sites	
• [name] – NYU Dept. of Neurology• [name] – NYU Multiple Sclerosis Comprehensive Care Center• NYU Langone Bernard and Irene Schwartz Center for Biomedical Imaging (CBI): [name]
Number of participants	N= 60
Statistical Analysis	Descriptive statistics, repeated measures ANOVA, simple correlations, and regression

CONFIDENTIAL

This material is the property of the NYU School of Medicine and Langone Medical Center. Do not disclose or use except as authorized in writing by the study sponsor

Drug/Device Template Version: 8 February 2019

Schematic of Study Design

CONFIDENTIAL

This material is the property of the NYU Langone. Do not disclose or use except as authorized in writing by the study sponsor
Observational Study Template Version: 8 February 2019

1 Key Roles

[name], PhD
Department of Neurology, NYU Langone Health
[name]
[name]
[contact]

[name], M.D.
Department of Neurology, NYU Langone Health
[name]
[name]
[contact]

[name].
NYU Langone Health —Radiology
[name]
[name]
[contact]

[name]
Department of Neurology, NYU Langone Health
[name]
[contact]
[contact]

[name]
Department of Neurology, NYU Langone Health
[name]
[contact]
[contact]

2 Introduction, Background Information and Scientific Rationale

2.1 Background Information and Relevant Literature

The goal of this project is to evaluate intra-individual variability (IIV) in cognitive performance, measured across response time (RT) on a computer task, as a marker of potential cognitive decline. We currently identify a patient's advancing neurological decline when it reaches the threshold for clinical detection of change. There remains an urgent need to identify patients before the onset of decline and disability¹. Our scientific premise is that the initial neuronal dysfunction that defines prodromal neurodegeneration²⁻⁵ can be reliably identified by subtle inconsistencies in cognitive processes⁶⁻⁸. We therefore propose using a clinically applicable approach to evaluate cognitive consistency as an indicator of prodromal neurological disability¹.

Cognitive consistency can be readily measured using simple computer-based psychomotor tasks⁹⁻¹², capturing intra-individual variability¹³⁻¹⁵ (IIV) across an individual's repeated reaction times (RTs). IIV, compared to the conventional measures of accuracy or speed¹⁶, is a highly sensitive marker of future health status at the population level^{8,17} as well as in prodromal neurological disease¹⁸⁻²¹.

CONFIDENTIAL

This material is the property of the NYU Langone. Do not disclose or use except as authorized in writing by the study sponsor
Observational Study Template Version: 8 February 2019

For this project, we propose to develop the measurement of IIV towards its clinical application as prodromal marker in MS. We will utilize an innovative and accessible approach to measure IIV in patients that provides an age-normative score to represent cognitive consistency interpreted at the individual level. We will measure IIV measured with the simple and choice RT tasks in the computer-based Cogstate⁹ platform. This brief (~7 min), practical, and widely available IIV measurement is clinically validated and with an extensive (n=95,162) normative data points for interpretation at the individual level. The cognitive IIV value will be compared to real time neuronal responses to tDCS as prodromal MS marker via a tDCS-MRI scan. This work will develop a clinical measure of IIV as behavioral measure of prodromal neurodegeneration that can guide early detection and, ultimately, prevention of disability.

2.2 **Rationale**

While we can detect cognitive impairment once it reaches the level of clinical impairment, there remains an urgent need for a measure that can identify patients *at risk* for impairment *before* the onset of disability. Our *scientific premise* is to measure risk in the prodromal/early stage- before disability occurs- by subtle inconsistencies in cognitive processes measured on simple computer-based reaction time tests. We will compare the IIV measure to neuroimaging markers of early disease. This work will advance us towards a clinical screening measure that can be used to detect the patients most at risk for near-term neurological disability in the context of MS.

3 Potential Risks & Benefits

3.1.1 Known Potential Risks

Risks associated with cognitive assessments and questionnaires: Completing questionnaires may produce some emotional distress in some participants. While we don't anticipate this will be a significant issue, participants will be allowed to take breaks as needed and may stop answering questions at any time without affecting their enrollment.

Risks associated with tDCS: There are no major risks associated with tDCS. Some people report head tingling, itchiness at the site of anodal stimulation, and a mild heating sensation. These irritations are usually mild and tolerable.

As in our previous MRI-tDCS study, we will use a Soterix Medical tDCS device (<https://soterixmedical.com/research/1x1/tdc>) to administer ~20 minutes of stimulation during the MRI scan. The Soterix 1x1 tDCS device is outside of the MRI suite in the MRI control area. The cables used to connect the tDCS device to the tDCS headset/electrodes (which will be inside the MRI suite) are MRI-certified carbon cables. In addition, between the MRI control room and the MRI suite is a patch panel with an MRI filter. So far, no tDCS sessions delivered during the MRI scan were aborted due to safety or tolerability concerns. The most commonly reported side effects were skin tingling, sensations of warmth, and skin itching.

For the reasons referenced above, tDCS meets the criteria for an abbreviated IDE (non-significant risk medical device):

1. It is **not** intended as an implant and **does not** present a potential for serious risk to the health, safety, or welfare of a subject
2. It is **not** purported or represented to be for a use in supporting or sustaining human life and **does not** present a potential for serious risk to the health, safety, or welfare of a subject.
3. It is **not** for a use of substantial importance in diagnosing, curing, mitigating, or treating disease, or otherwise preventing impairment of human health and **does not** present a potential for serious risk to the health, safety, or welfare of a subject: the device will not be used for subject treatment and subjects standard medical treatment will continue regardless of their participation in the study
4. It **does not** otherwise present a potential for serious risk to the health, safety, or welfare of a subject²³⁻²⁵.

CONFIDENTIAL

This material is the property of the NYU Langone. Do not disclose or use except as authorized in writing by the study sponsor
Observational Study Template Version: 8 February 2019

Risks associated with MRI

Magnetic Field and Imaging Risks: MRI scanning involves the use of a magnet and radio frequency waves (much like an ordinary short-wave radio). There are no known risks or adverse effects resulting directly from exposure to magnetic fields and radio frequency signals used in this study, other than the potential risks associated with the scanning procedure summarized below. These potential risks are present with any MRI procedure.

Implanted Devices: Subjects, who have pacemakers, certain aneurysm clips, or shrapnel fragments or persons with metal in the eye, are at risk for injury from MRI examinations.

Collision Hazard: Because of the strong magnetic field associated with the scanner, one risk is that of a metallic object flying through the air toward the scanner and hitting you. To reduce this risk, all people involved with this study will remove all metal from their clothing and all metal objects from their pockets when in the scanning environment.

Hearing Protection: The MRI scanner produces tapping sounds during operation, which may reach very loud levels. To minimize any discomfort from this noise, the subject will be provided with disposable earplugs that suppress external noise levels but do not eliminate voice communication with the scanner operator. Alternatively, in some cases, they will have headphones instead of earplugs, which will deliver other sounds.

Claustrophobia (Fear of confined spaces): Some people feel claustrophobic (fear of small spaces) in the MRI scanner. If this happens, the scan will be stopped immediately and the subject will be removed from the scanner.

Quench Hazard (MR system failure): The MR scanner uses liquid nitrogen and liquid helium. It is remotely possible that the liquid nitrogen and helium will boil off rapidly and fill the magnet room with extremely cold dense gaseous nitrogen and helium, which can be dangerous if breathed for more than a few moments. The scanner operator will obviously detect this and immediately provide assistance to anyone inside the magnet room.

During the MRI, subjects will be in visual and verbal contact with the experimenter throughout the scan through a video monitoring system and can be removed quickly. In addition, participants are given a squeeze ball so they can signal the scanner operator in the event of an emergency. Some subjects have experienced dizziness or a metallic taste if they move their heads rapidly in the magnet. This, however, is only temporary and does not occur if the head is still. Acoustical noise is generated by the charging and discharging of the gradient coils which create the magnetic fields used to generate an image. Subjects will be wearing hearing protection that reduces acoustic noise by approximately 30dB. All possible measures will be taken to educate research personnel concerning the dangers of metallic projectiles in the magnet room and any individuals entering the magnet room will be thoroughly screened for ferromagnetic material.

Risks associated with optional gait assessments

Completing the optional gait assessment is associated with minimal risks. To minimize these potential risks, we will ask the participant to perform only tests that are familiar with (walking, standing from sitting position).

3.1.1.1 Other risks

There is minimal risk of breach of confidentiality. All data will be obtained on paper CRF and kept strictly confidential and stored in locked cabinets located at [name]. Participants will be assigned a unique ID that will be used on all data collection instruments. The identifying link will be stored in a separate file and saved on password-protected NYU servers.

Unforeseeable Risks: While not expected, there may be risks associated with tDCS that are not known at this time.

CONFIDENTIAL

This material is the property of the NYU Langone. Do not disclose or use except as authorized in writing by the study sponsor
Observational Study Template Version: 8 February 2019

3.1.2 Known Potential Benefits

There is no direct benefit to the participants expected from participating in this study. It is hoped that developing a method for early identification of cognitive decline in MS can help patients and clinicians develop clinical treatment plans in the future.

3.1.2.1 Incidental findings

Incidental findings on MRI scans are possible health abnormalities that are found during the course of subjects' participation in this study and are unrelated to the research topic but may be important for subjects and their physician to know about. Incidental findings that are identified by licensed radiologists may or may not have clinical significance as determined by the health professionals conducting this study will be communicated to [name], Sub-I for this study, who will also review the neuroimaging reports.

If clinically useful information is uncovered, [name] will contact the subject on the telephone regarding the new information within 7 business days. Incidental findings reported to the subject will be recorded in the subject's medical record. A copy of the original image report will be provided upon patient request and participants will be encouraged to follow up with their treating physician outside of the study.

4 Objectives and Purpose

4.1 Primary Objective

The primary objectives are to characterize IIV and evaluate its underlying neuropathological mechanisms using neuroimaging techniques in prodromal/early MS. This work will develop a clinical measure of IIV as behavioral biomarker of prodromal MS that can guide early detection and, ultimately, prevention of disability.

4.2 Secondary Objectives

The secondary objective is to collect additional data to explore potential relationship among changes in IIV and cognitive function and in relation to gait variability.

5 Study Design and Endpoints

5.1 Description of Study Design

We will recruit 60 participants over a two-year period to assess the feasibility of developing the measurement of IIV towards its clinical application as prodromal marker of MS, and to test the association between IIV and the real-time neuronal responses to tDCS as prodromal MS marker via a tDCS-MRI scan.

Thirty-five (35) participants will complete 1 visit that will last approximately 3.5 hours. The visit will include consent, a cognitive assessment, an optional gait assessment, and a 1-hour MRI brain scan combined with 20 minutes of simultaneous tDCS. Participants may also complete the MRI on a separate visit.

Twenty-five (25) participants will complete 1 visit that will last approximately 1.5 hours (consent, cognitive assessment, and optional gait assessment). Procedures are exactly the same except that the tDCS-MRI will not be completed.

Group assignment will depend on eligibility, enrollment space (e.g. if one group reaches its target), and participant choice. The only difference between the two groups is that 1 group will have the MRI-tDCS procedure.

CONFIDENTIAL

This material is the property of the NYU Langone. Do not disclose or use except as authorized in writing by the study sponsor
Observational Study Template Version: 8 February 2019

6 Study Enrollment and Withdrawal

6.1 Inclusion Criteria for All Participants

In order to be eligible to participate in this study, an individual must meet all of the following criteria:

1. Ages 21-59 years old (inclusive)
2. Prodromal MS (defined by radiologically isolated syndrome \leq 6 months from first MRI or clinically isolated syndrome \leq 3 months from first clinical event)
3. MS diagnosis of \leq than 5 years

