6.2 Exclusion Criteria (All Participants)

An individual who meets any of the following criteria will be excluded from participation in this study:

1. Below average estimated premorbid cognitive functioning (based on WRAT-4 reading recognition standard z-score < 85).
2. Presence of severe cognitive impairment (based on SDMT age normative z-score <-3.0).
3. Primary psychiatric disorder that would influence ability to participate.
4. Current uncontrolled seizure disorder.
5. Current substance abuse disorder.
6. History of head trauma in the past year (e.g., head injury, brain surgery) or medical device implanted in the head (such as Deep Brain Stimulator) or in the neck (such as a Vagus Nerve Stimulator).
7. Pregnant or breastfeeding

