7.2 Study Visit

- Obtain written informed consent (approximately 25 minutes or however much time is needed)
- Study clinician confirms patient's diagnostic eligibility based on inclusion/exclusion criteria in-person at the research visit. Alternatively, this can be done via phone, Zoom or Webex, prior to the baseline visit. Patients seen clinically at the NYU MSCCC may have their diagnostic eligibility confirmed without speaking to the study clinician prior to the baseline visit.
- Complete self-reported questionnaire-- Patient Determined Disease Steps²⁶ (PDDS, 5 minutes)
- Complete cognitive assessment (Cogstate and BICAMS, 30 minutes)
- Complete self-report questionnaire (paper form) (15 minutes).
- (Optional for all participants) Gait assessment (approximately 20 minutes)
- [tDCS-MRI group only] Perform tDCS tolerability test (2 minutes)
- [tDCS-MRI group only] Complete tDCS-MRI scan (40 minutes to prepare for scan, change, etc. and 60 minutes for scan [including 20-minutes of tDCS]).

8 Study Procedures

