8.1.1 All Participants

- A study clinician will meet with the participant to confirm their eligibility according to the MS or prodromal MS inclusion criteria. Depending on patient and clinician availability, the clinician can either meet the patient in-person on the day of the research visit in a private room at NYU MSCC ([name], or [name]). Alternatively, the clinician can speak to the patient via phone, Zoom, or Webex prior to the baseline visit to confirm eligibility. Patients who are known to the NYU MSCCC can have their eligibility confirmed by a study clinician without meeting with the patient. Patients who have been diagnosed with MS less than five years and who receive their care from an external provider can provide their medical record or a letter from their neurologist indicating the date and nature of their MS diagnoses to confirm eligibility.
- Participants will complete a cognitive assessment (measures described in section 8.2).
- Optional gait assessment: Participants will have the option to complete a brief gait assessment administered by a trained study team member. Participants will be asked to walk at their self-selected speed back and forth for 2 minutes along a 30 meter hallway ([name], or [name]) in order to collect at least 30 steps to calculate the motor IIV. The gait assessment will be

CONFIDENTIAL

This material is the property of the NYU Langone. Do not disclose or use except as authorized in writing by the study sponsor
Observational Study Template Version: 8 February 2019

repeated twice. During one walking task, participants will wear an inertial sensor around their waist (G-Sensor, BTS Bioengineering), while during the other will wear the inertial sensor on their shoe (Runscribe). The inertial sensor used will depend on availability. Both devices connect to a study iPad via Bluetooth and obtain data such as walking speed, balance, and stride length, etc. Identifying information will not be saved to the iPad or the sensors.

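### Sections 6.1 and 6.2 are wrong as written: 6.1 requires both recent RIS/CIS and an MS diagnosis, and 6.2 sets a WRAT-4 z-score cut-off that excludes everyone

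*Combined protocol and SAP*

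**What the plan says.** **Inclusion.** Section 6.1 opens with the rule that "an individual must meet all of the following criteria". Item 1 is age. Item 2 is prodromal MS, defined as RIS no more than "6 months from first MRI or clinically isolated syndrome" no more than "3 months from first clinical event". Item 3 is an MS diagnosis of at most 5 years. Items 2 and 3 are numbered separately, and no 'or' joins them.

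Two other places describe the same population differently. The Population row of the Protocol Summary lists CIS, RIS, "or subjects with a MS diagnosis of less than 5 years". Section 8.1.1 has a study clinician meet the participant to "confirm their eligibility according to the MS or prodromal MS inclusion criteria". It also lets a patient with MS of under five years who is treated elsewhere qualify on a medical record or a neurologist's letter, and mentions no RIS/CIS window.

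**Exclusion.** Under Section 6.2, meeting any one criterion excludes. Item 1 is aimed at below-average premorbid functioning and is "based on WRAT-4 reading recognition standard z-score < 85". Item 2 is aimed at severe cognitive impairment and is "based on SDMT age normative z-score <-3.0".

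**Use at entry.** Section 7.2 has the clinician confirm "diagnostic eligibility based on inclusion/exclusion criteria in-person at the research visit", or remotely beforehand.

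**The concern.** These are decision rules, and each gives a wrong result when applied as worded. Section 6.1 shuts out RIS/CIS patients who have no MS diagnosis, and MS patients who are past the 6- or 3-month window. Those are the groups that the Protocol Summary and Section 8.1.1 describe as the cohort. The WRAT-4 criterion, read on the scale it names, shuts out everyone.

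Two things are at stake.

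- **What the cohort is.** Section 6.1 item 2 uses 'prodromal' for RIS/CIS only. The Protocol Summary uses it for early MS including diagnosed MS. Section 11.2 plans to enrol 60 people with prodromal MS. The documents therefore support three cohort definitions (both conditions, either condition, RIS/CIS only), and a reader of the results needs to know which one applies.
- **Compliance.** Section 14.3 counts any noncompliance with the protocol as a deviation, and Section 9.3.1 asks for IRB reporting within 5 working days of deviations that could recur. On the literal text, each enrolment of an intended MS-only or RIS/CIS-only patient is such a deviation. Section 6.7.1 also allows participation to be terminated for an exclusion criterion recognised late.

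**Working it through.** The plan gives no figure on this point to reproduce. The check is a truth table, a comparison of time windows and one normal probability.

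**Step 1: who qualifies under each reading of 6.1.** Age is taken as met.

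| Profile | Item 2 (recent RIS/CIS) | Item 3 (MS, at most 5 years) | All items (6.1) | Item 2 or item 3 (Summary, 8.1.1) |
|---|---|---|---|---|
| RIS/CIS only | yes | no | out | in |
| MS only | no | yes | out | in |
| Both | yes | yes | in | in |
| Neither | no | no | out | out |

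The 'or' reading admits three profiles and the literal reading admits one. The literal set is not empty, since a person can have a recent RIS or CIS and already carry an MS diagnosis.

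**Step 2: what is left of item 3's limit under the literal reading.** Inputs from 6.1: 6 months (RIS), 3 months (CIS) and 5 years (MS). Assumption, not in the documents: the MS diagnosis is not made before the first MRI (RIS route) or the first clinical event (CIS route). Time since diagnosis then cannot exceed item 2's window.

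- Item 3 window: 5 × 12 = 60 months.
- RIS route: 60 − 6 = 54 months unusable; 54/60 = 90%.
- CIS route: 60 − 3 = 57 months unusable; 57/60 = 95%.

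The 5-year limit therefore never binds when item 2 must also hold, which is further evidence that items 2 and 3 were meant as alternatives.

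**Step 3: the WRAT-4 cut-off.** On a z scale with normal scores, P(Z < 85) = 1.000, so everyone meets the exclusion. The item directly below it uses a workable z cut-off (−3.0), so the list does not use 'z-score' loosely throughout.

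If 85 is a standard score, the share of a normative population excluded depends on a scale that the documents do not state:

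- Assumed mean 100, SD 15: z = (85 − 100)/15 = −1.0, about 15.9% excluded.
- Assumed mean 100, SD 10: z = (85 − 100)/10 = −1.5, about 6.7% excluded.

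**Step 4: does another section correct the label?** No. Section 8.2 describes the WRAT-4 without a score scale. Section 11.3 names z-scores for IIV and the three BICAMS tests but not for the WRAT-4.

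**The case against.** The strongest reply is that the intent is plain and staff would follow it. Section 8.1.1 is the more specific instruction on how eligibility is confirmed, it says 'or', and the Protocol Summary agrees. The word 'standard', the below-average description and the value 85 all point away from a z scale, and a rule that excludes everyone would be noticed with the first participant. Section 7.2 concerns diagnostic eligibility, so it does not show that the clinician applies the WRAT-4 cut-off at that step. The study is exploratory, and Section 11.2 calls its sample size arbitrary, so no powered inference depends on the wording. The profile count and the percentages measure logic and calendar time, not an effect on enrolment, bias or power.

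Much of this is right. Intent is largely recoverable, Section 7.2 supports the inclusion point and not the WRAT-4 point, and the figures say nothing about patient frequencies. It does not remove the defects. The 'or' in Section 8.1.1 contradicts 6.1 and does not amend it: the formal inclusion list still says all. Section 6.2 makes the WRAT-4 cut-off binding by itself, without help from Section 7.2. Recoverable intent is also weaker for the WRAT-4, because the scale is stated nowhere.

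One further point stands. The Protocol Summary introduces its list as examples and gives no 6- or 3-month windows, so putting 'or' into 6.1 does not by itself make the two texts identical.

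**Conclusion.** The concern holds on both parts. Section 6.1 requires jointly what the Protocol Summary and Section 8.1.1 offer as alternatives, and so admits one of the three profiles that the 'or' reading admits. Section 6.2 item 1 excludes everyone on the scale it names. The 90% and 95% figures rest on the assumption that diagnosis does not precede the first MRI or first clinical event. The 15.9% and 6.7% figures rest on assumed score scales and only show why the scale must be stated.

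These are drafting errors in two operative rules and should be fixed. They do not show that the study cannot enrol, that screening was misapplied or that any analysis fails.

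**What to change.** 1. **Section 6.1:** reconcile it with the Protocol Summary and Section 8.1.1, so that eligibility reads as criterion 1 AND (criterion 2 OR criterion 3).
2. **Section 6.2 item 1:** remove 'z-' so that the rule refers to a standard score below 85. The sponsor should confirm this and state the score scale (mean and SD).
3. **In the same amendment:** align 'at most' 5 years (6.1) with 'less than' 5 years (Protocol Summary and 8.1.1). Give 'prodromal' one meaning across the Protocol Summary, 6.1 and 11.2. Make clear whether the 6- and 3-month windows apply to the RIS and CIS patients named in the Protocol Summary.

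The cost is a short wording amendment, which needs IRB approval under Section 13.2. Sample size, procedures and analysis stay as they are.
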